7. RESEARCH QUESTIONS AND OBJECTIVE(S)

Following the initiation of any ARV regimen containing CAB and/or RPV LA among PLWH, the study will aim to assess usage patterns, durability, discontinuation, and virologic outcomes.

The specific objectives are to:

- 1. Describe CAB and/or RPV LA containing regimens usage patterns
 - Descriptive analysis of study population by baseline demographic and clinical characteristics
 - Monitor for use of oral lead-in
 - The potential regimen combinations are listed below (Note that CAB+RPV LA is the only approved regimen)
 - a. CAB+RPV LA regimen only
 - b. CAB LA monotherapy
 - c. CAB LA use in combination with ARVs other than RPV LA
 - d. RPV LA monotherapy
 - e. RPV LA use in combination with ARVs other than CAB LA
 - f. CAB LA+RPV LA+other ARVs
 - g. Combined group b-f
- 2. Assess adherence, durability and discontinuation for persons starting CAB+RPV LA regimen;
 - Proportion of individuals discontinuing the regimens of interest will be assessed.
 - Reasons for discontinuation will be assessed.
 - Non-adherence to the dosing schedule will be assessed by:
 - a. Estimating the number of individuals that missed one or more consecutive injections without taking daily oral bridging therapy or any other oral ARV regimen while not on CAB+RPV LA containing regimens and mean and median number of injections missed during a 12-month period
 - b. Estimating the number of individuals who received the injections seven or more days later than their scheduled injection visit and median duration of delayed injections
 - c. Estimating the number of individuals who missed one or more consecutive injections without taking daily oral bridging therapy or those who received the injections seven or more days later than their scheduled injection visit (Combined group a OR b) and describe patient characteristics for the individuals that are nonadherent.
 - Number of individuals with incorrect route of administration will be described.

- 3. Assess the clinical effectiveness (i.e. proportion of individuals experiencing virologic failure) among PLWH who initiate CAB+RPV LA regimen
 - a. Estimate the proportion of individuals with virologic failure, during the first 6 months after initiation of CAB+RPV LA
 - b. Estimate the proportion of individuals with virologic failure, at 6, 12 and 24 months after initiation of CAB+RPV LA
 - c. Stratified analyses for 3a and 3b will be conducted for VL at regimen initiation (<50 copies/mL and ≥50 copies/mL).

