 - d. Assessment of VL for PLWH on other regimen combinations (b-f in objective 1) at 6, 12 and 24 months after initiation of the regimen
- 4. Monitor for resistance and next treatment response among individuals who discontinued CAB+RPV LA, where VL data are available and resistance testing has been done as part of routine clinical practise
 - Describe the ARV regimen individuals are switched to after discontinuation of CAB+RPV LA containing regimens
 - Monitor for resistance (where this has been done as part of routine clinical practise) during the 48 months following the switch
 - Describe virologic outcomes at 12, 24, 36 and 48 months after discontinuation of CAB+RPV LA containing regimens
- 5. Evaluate the effectiveness of routine risk minimisation measures for regimen adherence, discontinuation due to incorrect route of administration and off-label use of CAB+RPV LA regimen
 - Assess off-label use as described in objective 1
 - Estimate proportion of treatment naive or individuals not suppressed initiating regimen
 - Assess non-adherence to the dosing schedule as described in objective 2
 - Assess the frequency of discontinuation due to incorrect route of administration

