8.3. Clinical Variables

The EuroSIDA study collects a comprehensive range of variables, as summarised in Table 2 below.

Table 2. Variables routinely collected in the EuroSIDA Study

Demographics and basic information	Date of birth, date first seen at department, sex, country of origin, ethnicity, height, weight, date of first HIV-1-antibody positive test, mode of HIV-1 transmission, smoking status, alcohol abuse, drug user information, predisposition to MI or stroke among relatives
Infection-related Laboratory data	HIV-ribonucleic acid ("RNA"), HCV antibody test, HCV-RNA, HBsAg result, HBV-DNA, CD4 count, CD8 count, SARS-CoV-2 PCR and antibody

Other Laboratory data	total cholesterol, HDL, LDL, haemoglobin A1c (HbA1c) and/or glucose, triglycerides, serum creatinine, ALT, AST, bilirubin, albumin, INR, platelets, haemoglobin, proteinuria
Medical treatment	All ARV start and stop dates and reasons for discontinuation (including injection site reaction and injection fatigue) and treatment for HCV, hypertension, treatment for CVD and/or diabetes, Tuberculosis treatment, opioid maintenance therapy, dyslipidaemia incl. start and stop dates
Paraclinical data	Systolic and diastolic blood pressure, liver biopsy, fibroscan, DEXA scan, plasma samples
Clinical events	Syphilis, AIDS defining events (OIs including tuberculosis), myocardial infarction, stroke, diabetes, invasive cardiovascular procedures, end-stage liver disease, end-stage renal disease, AIDS and NADMs, liver and kidney transplantation, fractures

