8.3.1. Exposure definitions

The study period for data collection will start at the date of initiation of oral lead-in with CAB and/or RPV. The follow-up period for data analyses will start with first injection of CAB and/or RPV LA containing regimens and end at up to 48 months after discontinuation of the last injection.

Details about use of CAB and/or RPV LA containing regimens will be collected on a separate CRF. The data collected include dates of all planned and actual injections, use of oral bridging therapy for CAB+RPV LA, HIV subtype and resistance testing prior to initiation or at time of discontinuation of LA.

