8.3.2. Outcome definitions

1.Regimen discontinuations: Discontinuation of CAB+RPV LA regimen for any reason during the study period will be captured, tabulated and reported.

Individuals who receive the oral lead-in but never initiate the CAB+RPV LA regimen will be tabulated separately but not included in the primary analysis.

Discontinuation of CAB +RPV LA will be defined as the latest date of the next scheduled injection which is missed and where bridging therapy has not been started. For example, for monthly dosing, if the first injection of CAB+RPV LA was received on June 1st, the second injection should be received on July 1st (allowed time window for second injection is June 24th to July 8th). The third injection should follow the timing of the first injection and should be received on August 1st (allowed time window for third injection is July 25th to August 8th). If not, date of discontinuation will be defined as August 8th (Monthly dosing).

For every 2 month dosing, if the first injection of CAB+RPV LA was received on June 1st, the second injection should be received on July 1st (allowed time window for second injection is June 24th to July 8th). The third injection should follow the timing of the first injection and should be received on September 1st (allowed time window for third injection is August 25th to September 8th). If not, date of discontinuation will be defined as September 8th (Every 2 month dosing).

Discontinuation will also be captured, tabulated and reported for any other CAB and/or RPV containing regimen.

Durability will be measured as proportion of individuals continuing on the regimen at the end of 6, 12 and 24 months.

Adherence will be assessed by estimating the number of individuals that missed one or more consecutive injections without taking daily oral bridging therapy or any other oral ARV regimen while not on CAB+RPV LA regimen and mean and median number of injections missed during a 12-month period. We will also estimate the number who received the injections seven or more days later than their scheduled injection visit and median duration of delayed injections in persons using bridging therapy.

In the standard follow-up data collection in EuroSIDA reasons for discontinuation are recorded as below.

Table 3. EuroSIDA – Reasons for Treatment Discontinuation

Code	Reason for Stopping Treatment
1	Treatment failure (i.e. virological, immunological, and/or clinical failure
1.1	Virological failure

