1.2	Partial virological failure
1.3	Immunological failure - CD4 drop
1.4	Clinical progression
1.5	Resistance (based on test result)
2	Abnormal fat redistribution
3	Concern of cardiovascular disease
3.1	Dyslipidaemia
3.2	Cardiovascular disease
4	Hypersensitivity reaction (skin eruption etc.)
5	Toxicity, predominantly from abdomen/G-I tract
5.1	Toxicity - GI tract
5.2	Toxicity - Liver
5.3	Toxicity - Pancreas
6	Toxicity, predominantly from nervous system
6.1	Toxicity - peripheral neuropathy
6.2	Toxicity - neuropsychiatric
6.3	Toxicity - headache
7	Toxicity, predominantly from kidneys

8	Toxicity, predominantly from endocrine system
8.1	Diabetes
9	Haematological toxicity (anemia etc.)
10	Hyperlactataemia/lactic acidosis
11	Bone toxicity
15	Social contra-indication
16	Contra-indication unspecified
16.8	Contra-indication expired
16.9	Contra-indication – other
17	MTCT regimen completed
70	Pregnancy - toxicity concerns (during pregnancy)
75	Pregnancy - switch to a more appropriate regimen for PMTCT
88	Death
90	Side effects - any of the above but unspecified
90.1	Comorbidity
91	Toxicity, not mentioned above
91.1	Toxicity, unspecified
92	Availability of more effective treatment (not specifically failure or side effect related)
92.1	Simplified treatment available
92.2	Treatment too complex
92.3	Drug interaction
92.31	Drug interaction - commencing TB/BCG treatment
92.32	Drug interaction - ended TB/BCG treatment
00.00	Change in eligibility criteria (e.g. child old enough for tablets; refrigerator no longer
92.33	available)
92.4	Protocol change
92.5	Regular treatment termination (used in tblMED e.g. for DAA's against HCV, antibiotics)
92.5	End of empiric treatment
92.0	Change in treatment not due to side-effects, failure, poor adherence or contra-
92.9	indication
92.91	Change to generic drug
92.92	Change to branded drug
93	Structured Treatment Interruption (STI)
93.1	Structured Treatment Interruption (STI) - at high CD4
94	Individual's wish/decision, not specified above
94.1	Non-compliance
94.2	Defaulter
95	Physician's decision, not specified above
96	Pregnancy (see also more specific codes 70 and 75
96.1	Pregnancy intended
96.2	Pregnancy ended
97	Study treatment
97.1	Study treatment commenced
97.2	Study treatment completed

97.6	Drug not available
98	Other causes, not specified above
	Incorrect route of administration
	Injection fatigue (not related to safety)
	Injection Site Reaction
	Lost to follow-up
99	Unknown

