case of resumption of LAI after missed second injection in two months or less, we will still consider it first exposure.

Similarly, the third injection (and injections thereafter) for the two-month schedule is given two months after the second injection and hence we will allow four months after the second injection to see if the regimen was resumed (≤3 months) or re-initiated (>3 months). In case of resumption of LAI after missed third injection in three months or less, we still consider it first exposure.

Treatment with long-acting antiretroviral therapy

Which long-acting antiretroviral drugs have been initiated? (drop down menu)

1) long acting cabotegravir + long acting rilpivirine

2) long acting cabotegravir without rilpivirine

3) long acting rilpivirine without cabotegravir

Dosage: 400/600 mg (CAB) / 600/900 mg (RPV) (drop down

menu)

Date of first injection: Year/month/day

Intended dosing schedule of long-acting antiretroviral therapy Monthly/Every 2 Month

HIV resistance testing (only pops up for the first injection and if CAB + RPV has been selected)

Has a HIV resistance test been performed prior to initiation of long-acting cabotegravir + rilpivirine yes/no

If yes

Date of latest most recent resistance test prior to initiation of long-acting antiretroviral therapy Year/month/day

Method used drop down menu

Please upload a copy of the resistance test report (result will be based on central review)

(After completion of date of first injection, a new section will open for second injection with target date one month after the first injection. All the questions below refer to subsequent injections after the first)

Has the patient received the next planned injection with long-acting antiretroviral drugs yes/no

If yes, Which long-acting antiretroviral drugs were given? (drop down menu)

1) long acting cabotegravir + long acting rilpivirine

2) long acting cabotegravir without rilpivirine

3) long acting rilpivirine without cabotegravir

Dosage: 400/600 mg (CAB) / 600/900 mg (RPV) (drop down

menu)

Date of injection: Year/month/day

Intended dosing schedule of long-acting antiretroviral therapy Monthly/Every 2 Month

(if the patient switches from monthly to two-monthly injections or vice versa, a new question pops up)

Reason for switching to monthly (or 2 monthly) injection schedule (drop down menu)

- 1. Convenience
- 2. To reduce cost
- 3. To reduce side effects
- 4. Personal reasons
- 5. Other (+ text field)

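### Objective 2 promises a count of people injected by the incorrect route, but the only structured item naming route is a reason for stopping, so wrong-route injections in people who continue are not systematically recorded

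*Protocol*

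**What the plan says.** The protocol names two quantities concerning route.

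- **Objective 2** (section 7), with the same sentence under Aim 2 in section 8.6: "Number of individuals with incorrect route of administration will be described". No restriction to people who stop is attached.
- **Objective 5** (section 7): "Assess the frequency of discontinuation due to incorrect route of administration". The abstract and Aim 5 in section 8.6 also tie route to discontinuation.

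The data sources are these:

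- **Section 8.3.1**, on the study-specific CRF: "The data collected include dates of all planned and actual injections, use of oral bridging therapy for CAB+RPV LA, HIV subtype and resistance testing". Route is not listed.
- **Table 2** (section 8.3), on routine medical treatment data: start and stop dates and stop reasons for all antiretrovirals. Route is not listed.
- **Table 3** (section 8.3.2), introduced by "In the standard follow-up data collection in EuroSIDA reasons for discontinuation are recorded as below", carries the entry "Incorrect route of administration".
- **Annex 1**: each later injection begins with "Has the patient received the next planned injection with long-acting antiretroviral drugs yes/no". If yes, the form asks for drug, dosage, date and intended schedule, plus a reason if the schedule changes. If no, it asks about bridging and restart, and it offers the menu of stop reasons only where long-acting therapy was not restarted.

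**The concern.** A wrong-route injection and a discontinuation because of one are different events, and the second is a subset of the first. Objective 2 asks for the first, while the data items support only the second. If the study is run as written, the figure reported under Objective 2 will leave out everyone who continued after such an injection. It will also leave out anyone who stopped but whose stop was coded under another reason.

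The error runs in one direction. Aim 5 describes its purpose as checking whether label guidance is followed. A very low Objective 2 count printed in the same report could be taken as evidence of correct administration, when the form had no systematic way to record an administration error short of stopping.

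**Working it through.** The protocol states no figure on this point, so there is nothing to reproduce. The check is to follow one case through the form and then express the result as a formula.

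**Tracing a case.** Suppose a person receives an injection by the wrong route and later returns for the next one.

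1. The injection was given, so the site answers yes in Annex 1.
2. The block that opens asks for drug, dosage, date and intended schedule. It has no route or administration-error item. The first-injection block also lacks one; it adds only a question on prior resistance testing.
3. The form moves on to the next injection. The stop-reason menu is not reached, because that needs a planned injection that was not given and no restart.
4. Routine EuroSIDA follow-up adds nothing, because Table 2 and Table 3 record reasons only when a drug is stopped.
5. Section 10 says individual-level adverse events and incidents will not be collected, so there is no separate safety channel.

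Suppose instead that the person stops. The case is counted only if the site picks the incorrect-route entry. If another reason is entered, such as virological failure or injection site reaction, it is missed.

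**As a formula.** Let N be the number of users, w the share ever given a wrong-route injection, and c the share of those who stop with that reason coded.

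- Objective 2 as worded: N × w
- Objective 2 as measurable, which is also Objective 5: N × w × c
- Share missed: 1 − c

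**Illustration only.** The protocol gives neither w nor c; both are assumptions. N is taken from the Table 4 scenarios.

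| N | w | True count | c | Counted | Reported share |
|---|---|---|---|---|---|
| 500 | 2% | 500 × 0.02 = 10 | 10% to 50% | 1 to 5 | 0.2% to 1.0% |
| 1000 | 2% | 1000 × 0.02 = 20 | 5% to 20% | 1 to 4 | 0.1% to 0.4% |

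At c = 0 none are counted, and at c = 1 all are. Nothing in the protocol narrows that range.

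**The case against.** The strongest reply is that the Objective 2 sentence is loose shorthand for the discontinuation count. Objective 2 is itself partly about discontinuation, and the abstract's version of it does not mention route. In section 8.6, the Aim 5 text on off-label users says discontinuation for incorrect route is assessed as under Aim 2. The only sentence there that names route is the unrestricted one. On that reading no data item is missing and only the wording is off. This is a plausible account of the intent, but it does not remove the problem. The sentence appears twice without restriction, Objective 5 uses the narrower wording, and the cross-reference runs the two together. Aim 2 also says stop reasons are taken as reported to EuroSIDA, so the cross-reference could be meant for that sentence instead. A reader cannot tell which count will be reported.

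Three stronger readings are tempting, and the protocol does not support them.

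- **That the risk-minimisation objective fails.** It does not. Objective 5 names discontinuation attributed to incorrect route, and Table 3 has an entry for exactly that.
- **That such injections can never come to light.** Annex 1 has free-text 'other' answers for starting bridging and for switching schedule, and the list in 8.3.1 is not stated to be exhaustive. A case could surface by chance. Those fields open only in those situations and do not ask about route, so they cannot yield a count.
- **That most cases are missed.** No figure in the protocol supports any particular capture share.

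It is also fair to say that a new CRF item would not be perfect. Data come from medical records, and section 8.8 already warns about quality when data are collected retrospectively on additional forms. An unnoticed error would still be entered as correct or as not documented.

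**Conclusion.** The concern holds as a mismatch between the Objective 2 and Aim 2 wording and the data items. As written, the Objective 2 count reduces to the Objective 5 count. It omits wrong-route injections that do not lead to a discontinuation coded that way, so it is an undercount of unknown size. The conclusion rests on the CRF in Annex 1 and the lists in 8.3, 8.3.1 and 8.3.2, not on the assumed rates above.

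The consequence is limited. This is one descriptive count with no hypothesis, model or precision target behind it. Objective 5 can be delivered as worded, and no analysis of effectiveness, durability, adherence to schedule or resistance changes. It should still be settled in the protocol, because the gap is in the annexed form and an analysis plan cannot recover data that were not collected.

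**What to change.** **Preferred.** Add one item to every injection block in Annex 1, covering the first injection, later injections and restarts: 'Administered by the intended route? yes / no / not documented'. Add route to the list in 8.3.1. Report Objective 2 from this item, with the share not documented beside it, and Objective 5 from the stop reason. State that the count covers the period in which injections are collected, which Annex 1 sets at 24 months plus six weeks. In Aim 5, replace the general reference to Aim 2 with the specific source for each count.

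**Otherwise.** Reword Objective 2 and Aim 2 to 'discontinuations attributed to incorrect route', which also resolves the Aim 5 cross-reference. State in 8.8 that wrong-route injections not leading to discontinuation are not captured.

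**Cost.** The first option adds one drop-down to records the form already opens, with slightly more site entry and some undocumented answers. The protocol does not say whether the HICDEP transfer format can carry the item, so that needs checking for sites that submit that way. The second option costs only a few words, but gives up any estimate of incorrect route as such.

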8. RESEARCH METHODS

8.1. Study Design

A prospective observational cohort study nested within the EuroSIDA study, using data from individual medical records from participating clinical sites will be conducted over a period of five years to meet the study objectives.

This study will be conducted through collaboration with EuroSIDA, a well-established, prospective observational cohort study of more than 13,000 individuals under active follow up in over 100 hospitals in 34 European countries, and Israel and Argentina [1].

For this non-interventional study, treatment and laboratory testing decisions will be made by the treating physician according to standard practice, taking into account the treatment history, individual characteristics, the approved SmPc for CAB+RPV oral and LA

formulations, contemporary regimen and local guideline or recommendations. All individuals who discontinue the regimen for any reason, will be followed for up to 48 months after discontinuation. The study protocol will be implemented by the EuroSIDA coordinating center.

8.2. Study Population and Setting

Study Population:

The study population will include PLWH over the age of 18 years, from EuroSIDA clinical sites who are new users of CAB and/or RPV LA containing regimens over a period of 5 years. Persons will be eligible for inclusion from the date of starting the treatment regimens after approval and commercial availability of the regimens. Only the first exposure to CAB and/or RPV LA containing regimens will be included in the primary analyses.

The potential regimen combinations are listed below (Note that CAB+RPV LA is the only approved regimen):

- a. CAB+RPV LA regimen only
- b. CAB LA monotherapy
- c. CAB LA use in combination with ARVs other than RPV LA
- d. RPV LA monotherapy
- e. RPV LA use in combination with ARVs other than CAB LA
- f. CAB LA+RPV LA+other ARVs
- g. Combined group b-f

EuroSIDA Cohort description:

The EuroSIDA study was initiated in 1994 and is a prospective observational cohort study of more than 22,000 individuals followed in over 100 hospitals in 34 European countries, and Israel and Argentina. The main objective of the study is to assess the impact of ARV drugs on the outcome of the general population of PLWH living in Europe.

In EuroSIDA, annual data collection is performed directly from clinics on individuals using comprehensive standardized clinical record forms via REDCap or electronic data transfer using the HICDEP format that includes information on outcomes and covariates [2]; further information is available at https://www.hicdep.org/. For each person, the date of starting and stopping each ARV drug is recorded. ATC codes for all ARVs and most non ARVs are collected. Dates of diagnosis of all AIDS defining diseases are recorded, using the 1993 clinical definition of AIDS from the Centers for Disease Control and Prevention. All EuroSIDA data undergo extensive data checks, queries and central clinical event validation to ensure a high quality and completeness of data.

Table 1. EuroSIDA currently contributing countries and geographical regions

Southern	Central Western	Northern Europe	Central Eastern	Eastern
Europe	Europe		Europe	Europe
Spain	France	United Kingdom	Poland	Estonia
Portugal	Belgium	Ireland	Czech Republic	Lithuania
Italy	Luxembourg	Netherlands	Bosnia-Herzegovina	Belarus
Greece	Switzerland	Denmark	Hungary	Ukraine
	Austria	Sweden	Romania	Russia
	Germany	Norway	Serbia	Georgia
		Finland	Slovenia	
		Iceland	Croatia	
*Israel			Albania	
*Argentina			North Macedonia	

^{*}non-European countries

Data Collection:

Following the approval and commercial availability of CAB+RPV LA, the study will collect prospective data on individuals initiating CAB and/or RPV LA containing regimens, over the course of 5 years. The EuroSIDA coordinating center will receive data from the clinical sites per the protocols established for data collection.

An additional data collection form will be used to enhance the routinely collected data from clinical sites. Dates of treatment, documented history of resistance at regimen initiation, resistance and HIV subtype data at virologic failure and after discontinuation and switching to another ARV regimen will be collected via the enhanced data collection using study specific additional CRFs. The additional CRF will collect baseline data at regimen initiation, 6 months, 12 months & 24 months for all individuals on the CAB and/or RPV LA containing regimen of interest and at 12 months, 24 months, 36 months & 48 months for those who discontinue the regimen and switch to other ARV regimens.

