Descriptive analyses will compare those with and without virologic failure to assess any differences in baseline characteristics of the two groups. Detailed analysis of additional risk factors will be limited to persons with 6, 12 or 24 months of follow-up. Multivariable logistic regression models will investigate the factors associated with virologic failure at 6 months, 12 months and 24 months after CAB+RPV LA initiation. Potential explanatory variables are listed above. We will also investigate the impact of missed doses and use of oral bridging therapy by using the data collected via the CRF. Multivariate analyses will be performed when > 30 persons on CAB+RPV LA have virologic failure and analyses will be limited to persons with > 6-, 12- or 24-months follow-up. The model building strategy will follow EuroSIDA protocol and include variables significant in univariate analyses as well as *a priori* pre-specified variables of interest. Primary analysis for clinical effectiveness will include individuals on CAB+RPV LA, with VL of <50/copies/mL at regimen initiation. In addition, all the analyses will be conducted separately for individuals on CAB+RPV LA with VL of ≥50 copies/mL at regimen initiation.

Our primary analyses of virologic outcomes will censor follow-up at discontinuation of CAB+RPV LA, last visit or death, whichever occurs first, an on-treatment approach to analysis. Sensitivity analyses will use an intent to treat approach and virologic outcomes will be assessed regardless of regimen discontinuation.

We will perform additional sensitivity analysis limited to those who start CAB+RPV LA with resistance data available, to confirm no present or past evidence of viral resistance to, and no prior virological failure with agents of the NNRTI and INSTI class.

AIM 4. Monitor for resistance and next treatment response among individuals who switched off CAB+RPV LA regimen

Monitoring for resistance

Since this is a non-interventional study aiming to capture individual care in real world setting, the study will not mandate resistance testing following discontinuation of the regimen of interest. Health care providers following the local treatment guidelines decide

what laboratory and resistance tests are to be conducted. Data thus generated will be captured and analyzed by the study team.

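### The 12–48 month form after stopping CAB+RPV LA is limited to people who switch regimen, while follow-up covers all who discontinue, leaving resistance data for non-switchers under conflicting rules

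*Protocol*

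**What the plan says.** Who is followed after stopping is described in several ways.

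- **Section 8.1 (Study Design):** "All individuals who discontinue the regimen for any reason, will be followed for up to 48 months after discontinuation". Section 8.3.1 likewise ends follow-up at up to 48 months after the last injection, with no condition on a new regimen.
- **Section 8.2 (Data Collection):** the additional CRF is due "at 12 months, 24 months, 36 months & 48 months for those who discontinue the regimen and switch to other ARV regimens". The preceding sentence, on what the CRF collects, also ties resistance and subtype data after treatment to both stopping and switching.
- **Section 7, objective 4:** "Monitor for resistance and next treatment response among individuals who discontinued CAB+RPV LA, where VL data are available", with the further proviso that resistance testing was done in routine practice. Within this objective, resistance is monitored "during the 48 months following the switch", while the virologic item reads "Describe virologic outcomes at 12, 24, 36 and 48 months after discontinuation of CAB+RPV LA containing regimens".
- **Section 8.6, Aim 4 heading:** "Monitor for resistance and next treatment response among individuals who switched off CAB+RPV LA regimen". The title-page table and the Abstract also use the switching wording for objective 4.
- **Annex 1:** collection of resistance results is prompted by discontinuation coded as treatment or virological failure (reasons 1, 1.1, 1.2), supplemented by checks for viral load above the limit of detection. Reminders go out 1 and 2 years after failure. No switch is required.

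**The concern.** A person who stops the injections and starts no other regimen belongs to the population of Sections 8.1 and 8.3.1 but not to the CRF schedule of Section 8.2. The protocol expects such people. Annex 1 lists a decision to stop injections separately from a switch to a different regimen. Table 3 has stop reasons for structured interruption (93), non-compliance (94.1) and default (94.2). Section 8.3.2 defines discontinuation by a missed injection without bridging therapy, which can include people on no ART.

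This group matters for the study's purpose. Section 6.1 stresses the need for a suppressive regimen after stopping, and Section 6.2 gives resistance after missed doses as part of the rationale. Starting new ART is itself an event after discontinuation and is plausibly related to viral load and resistance. Collecting resistance data only from those who start it would select on something linked to the outcome.

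**Working it through.** The plan states no rate or sample size on this point, so there is no figure to reproduce. The check compares the sections for each type of data, taking a person who stops and starts no new ART.

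| Data item | Where collected | Does it require a switch? | Time origin |
|---|---|---|---|
| Viral load | Routine (Table 2); all information on each individual since the last capture (Section 8.5.2) | No | Discontinuation (objective 4; Aim 4, next treatment response) |
| ARV start and stop dates | Routine (Table 2); also on the additional CRF | No | n/a |
| Resistance and subtype, 12–48 month CRF | Additional CRF (Section 8.2) | Yes | The switch (objective 4; most of Aim 4) |
| Resistance form | Annex 1 | No; needs a failure code or a viral load flag | Failure (reminders at 1 and 2 years) |

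**Viral load.** Section 8.2 describes the role of the form thus: "An additional data collection form will be used to enhance the routinely collected data from clinical sites". Viral load is not in its listed content. HIV-RNA reaches the coordinating centre whether or not a new regimen is started, and Aim 4 describes virologic success from discontinuation with no condition on new ART. The route for non-switchers is open.

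**Resistance.** Resistance results do not appear in Table 2; Section 8.2 assigns them to the additional CRF. Under that schedule a non-switcher has no form at 12, 24, 36 or 48 months. Under objective 4 the 48-month window has no starting date for that person. Aim 4 is itself mixed: it counts resistance after failure from the switch, but cumulative resistance from stopping. Annex 1 would catch some non-switchers, namely those with a failure code or a flagged viral load. Its reminders stop at 2 years, against a 48-month schedule, and the protocol does not say whether the viral load checks continue after discontinuation.

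**Size, conditional only.** Suppose Aim 4 success were reported among switchers only. Let f be the share of discontinuers with no new ART, and p_s and p_n the success proportions with and without new ART:

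overstatement = p_s − [(1 − f)·p_s + f·p_n] = f·(p_s − p_n)

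All three inputs are assumed; the protocol gives none. I take p_s − p_n between 0.85 − 0.30 = 0.55 and 0.95 − 0.00 = 0.95.

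| f | × 0.55 | × 0.95 |
|---|---|---|
| 2% | 1.1 points | 1.9 points |
| 5% | 2.75 | 4.75 |
| 10% | 5.5 | 9.5 |
| 20% | 11 | 19 |

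If routine viral loads of non-switchers are used, as Table 2, Section 8.5.2 and Aim 4 allow, this mechanism contributes 0. The table shows what would follow from one reading of the text. It does not estimate a bias in the plan as written.

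**The case against.** The strongest reply is that only a supplementary form is restricted. Viral loads and ARV dates come in routinely for everyone, virologic success is anchored at discontinuation, and Aim 4 separately describes the time to the next regimen. Its switching wording may simply mean stopping, since the section uses the terms interchangeably. The Annex 1 resistance form asks for tests after discontinuation and needs no switch. Objective 4 was always limited to people with available data, and next treatment response naturally concerns people who have a next treatment.

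Most of this stands for viral load. A reader might infer that people without new ART drop out of objective 4 and that virologic success is therefore overstated. The documents do not support that: nothing explicitly limits the success denominator to switchers, and any percentage-point figure presupposes the exclusion it is meant to show.

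The reply is weaker for resistance. Those results are not routine variables, Section 8.2 states the switch condition in two adjoining sentences, and Annex 1 distinguishes stopping from switching, so the words are not plainly synonyms. The Annex 1 form differs from Section 8.2 in trigger, time origin and duration. It adds a third rule and does not resolve the conflict. The proviso on available data limits objective 4 to tests done in routine care; it does not justify leaving such tests uncollected because no switch followed.

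**Conclusion.** The inconsistency is real and should be corrected. Sections 8.1 and 8.3.1, Section 8.2 and Annex 1 give three different rules for whose data are collected after CAB+RPV LA stops. Objective 4 and Aim 4 use two time origins, one of which is undefined for people who start no new ART. The direct consequence is that resistance and subtype data for those people may be incomplete, in a study where Section 8.8 already expects few and selectively tested resistance results.

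Overstated virologic success is a possible risk only, dependent on a switchers-only reading of the Aim 4 denominator. Its size cannot be derived from the protocol: it is 0 if routine viral loads are used, and about 1 to 19 points under the assumed inputs above if non-switchers are left out. The loss of resistance data cannot be sized either, since the protocol gives neither the share of discontinuers without new ART nor how often they are tested.

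**What to change.** 1. **Section 8.2:** remove the switch condition from the 12–48 month CRF schedule, and in the preceding sentence tie post-treatment resistance and subtype data to discontinuation alone.
2. **Section 7, objective 4, and Section 8.6, Aim 4:** time resistance monitoring from discontinuation, replacing "during the 48 months following the switch" and the matching Aim 4 phrases.
3. **Aim 4 heading:** use *discontinued* in place of *switched off*, to match Section 7, and make the same change in the title-page table and the Abstract.
4. **Annex 1:** align the resistance form and its reminders with the 12, 24, 36 and 48 month schedule for all who discontinue.
5. **Reporting:** state that all discontinuers are the Aim 4 denominator, show people with no new ART at each time point as a category, and give response among switchers as a labelled subset.

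The cost is protocol and CRF wording plus a few extra forms for people already in the cohort. No testing is mandated; only tests done in routine care are collected. Non-switchers will probably have more missing data, and its extent should be reported by category at each time point.
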